9.4.1. Guidance for Cardiac Monitoring Following Treatment Re-Initiation

If the dose is interrupted for ≥ 7 days, upon re-initiation of treatment subjects are to have cardiac monitoring performed. Predose vital signs (resting heart rate, systolic and diastolic blood pressure (BP), body temperature, and respiratory rate) will be used for comparison to postdose measurements. Re-initiation of study treatment should occur before 12:00 PM (noon).

First Dose Cardiac Monitoring

In-clinic cardiac monitoring, of at least 4 hours, will occur on the day of treatment re-initiation, and will include the following (Table 3):

- Full vital signs (heart rate, systolic and diastolic BP, body temperature, and respiratory rate) and a 12-lead ECG (taken with the subject in the supine position) will be assessed predose
- After the first dose of study treatment following re-initiation, subjects must remain under observation in the clinic for at least 4 hours

- At Hours 1, 2, and 3 (± 15 minutes) postdose, the heart rate and systolic and diastolic BP will be assessed with the subject in the sitting position, with the time recorded. If the subject has a heart rate < 50 bpm or if cardiovascular symptoms develop, then the subject should remain closely monitored, including 12-lead ECGs as clinically indicated, until the Hour 4 discharge assessment
- At the Hour 4 (± 15 minutes) discharge assessment, heart rate and systolic and diastolic BP will be assessed with the subject in the sitting position and a 12-lead ECG (with the subject in the supine position) will be performed. Subjects may be discharged from the clinic after the 4-hour assessment if they meet the criteria described in Table 4. Subjects not meeting the discharge criteria will require extended monitoring as described below
- Subjects experiencing a clinically relevant treatment-related symptomatic event (eg, chest pain, dizziness, palpitations, or syncope) associated with reduction of the heart rate or clinically relevant 12-lead ECG changes at any time during the 4-hour monitoring period must be discontinued from treatment (Table 5)

Table 3: Procedures to be Performed During the Monitoring Period

Procedure	Predose	Hours 1, 2, 3 Postdose ^a	Hour 4 Postdose ^a
Blood pressure and heart rate ^b	X	X	X
12-lead ECG	X		X
Assess discharge criteria			X

^a Measurements may be taken \pm 15 minutes of the scheduled time.

ECG, electrocardiogram

Table 4: Discharge Criteria After Cardiac Monitoring

Subjects will be released from the clinical site after dosing on the first re-initiation day (but no sooner than 4 hours postdose) when they fulfill the following discharge criteria:

- Heart rate \geq 50 bpm or no more than 10 bpm lower than the predose (baseline) value
- No evidence of second-degree AV block or higher
- No cardiac symptoms (eg, chest pain, dizziness, palpitations, lightheadedness, shortness of breath, or syncope)

Note: Subjects should have written instructions on when to return to the clinic and a 24-hour contact phone number to call in the event of any new or worsened cardiovascular symptoms.

AV, atrioventricular

Extended Cardiac Monitoring

Subjects who do not meet discharge criteria at 4-hours postdose will require extended cardiac monitoring:

• Vital signs will be assessed hourly and 12-lead ECG may be performed, as clinically indicated, until the subject meets the discharge criteria (Table 4).

^b Heart rate is based on vital signs

- The Medical Monitor should be contacted if the subject does not meet the discharge criteria after ≥ 4 hours of extended cardiac monitoring.
- Any subject who requires extended monitoring on the first re-initiation day must return on the second re-initiation day for the second dose and will be re-monitored as on the first day. These subjects will be discontinued from study treatment if they do not meet the discharge criteria at 4 hours after the second re-initiation dose. Extended cardiac monitoring should be continued until the subject meets the discharge criteria (Table 4).
- Subjects experiencing a symptomatic event (eg, chest pain, dizziness, palpitations, lightheadedness, shortness of breath, or syncope) at any time during the 4-hour monitoring period that is not associated with either a reduction in heart rate or clinically relevant change in 12-lead ECG, may be discharged provided they meet the discharge criteria (Table 4), and as deemed appropriate by the Investigator; however, these subjects must return on the second re-initiation day for the second dose and will be re-monitored as on the first day. These subjects must be discontinued from treatment if they do not meet the discharge criteria at 4 hours after the second re-initiation dose and extended cardiac monitoring should be continued until the subject meets the discharge criteria (Table 4).

Study Treatment Discontinuation Related to Postdose Cardiac Monitoring

A complete list of reasons for study treatment discontinuation is provided in Section 5.1. Reasons for study treatment discontinuation specific to postdose cardiac monitoring are provided in Table 5. The Medical Monitor should be contacted before discontinuing a subject.

Table 5: Discontinuation of Study Treatment Related to Postdose Cardiac Monitoring

Reasons for Study Treatment Discontinuation Related to Postdose Cardiac Monitoring^a

- Subjects who have a cardiovascular treatment-related symptomatic event (eg, chest pain, dizziness, palpitations, lightheadedness, shortness of breath, or syncope) associated with reduction of the heart rate or associated with clinically relevant 12-lead ECG changes at any time during the 4-hour monitoring period on the first and second re-initiation days (as applicable).
- Subjects who have not met the discharge criteria on the first re-initiation day after ≥ 4 hours of extended monitoring, or on the second day by 4 hours postdose.

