5. REMOVAL OF SUBJECTS FROM STUDY TREATMENT OR ASSESSMENT

5.1. Discontinuation from Study Treatment

A subject's double-blind treatment may be discontinued for any of the following reasons:

- Worsening of disease (Note: If a subject discontinues double-blind treatment at any time, the subject may be eligible to enter the APD334-303 OLE study [Section 5.1.1])
- Adverse event that in the judgement of the Investigator and/or Medical Monitor the subject should not continue study treatment
- Subject noncompliance with the protocol or study treatment that is considered significant by the Medical Monitor
- Investigator decision
- Withdrawal by subject or parent/guardian
- Lack of efficacy
- Lost to follow-up
- Study termination by Sponsor
- Other, non-adverse event

A subject's double-blind treatment must be discontinued for any of the following reasons:

- Decline in PFT values (forced expiratory volume at 1 second [FEV₁] and/or forced vital capacity [FVC]) below 50% of the predicted values
- Confirmed diagnosis of clinically significant macular edema
- Confirmed diagnosis of active tuberculosis (TB)
- Subjects who have a cardiovascular treatment-related symptomatic event (eg, chest pain, dizziness, palpitations, lightheadedness, shortness of breath, or syncope) associated with reduction of the heart rate or associated with clinically relevant ECG changes at any time during the 4-hour monitoring period on the first or second day after re-initiation of treatment after a dose interruption of ≥ 7 days (Section 9.4.1)
- Subjects who have not met the discharge criteria on the first day of re-initiation of treatment after ≥ 4 hours of extended monitoring, or on the second day of re-initiation by 4 hours postdose.
- Pregnancy (Section 9.8.9)
- Suspected drug-induced liver injury as defined by the 2009 FDA Guidance for Industry (FDA 2009):
 - Alanine aminotransferase (ALT) or aspartate aminotransferase (AST) > 8 × upper limit of normal (ULN)
 - ALT or AST $> 5 \times ULN$ for > 2 weeks

- ALT or AST $> 3 \times$ ULN and (total bilirubin $> 2 \times$ ULN or international normalized ratio > 1.5)
- ALT or AST $> 3 \times$ ULN with the appearance of fatigue, nausea, vomiting, right upper quadrant pain or tenderness, fever, rash, and/or eosinophilia (> 5%)

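### Both second-dose return instructions in Protocol 9.4.1 lack an exception for subjects whom Section 5.1 and Table 5 require to be stopped on the first re-initiation day

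*Protocol*

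**What the plan says.** Protocol 9.4.1 governs re-initiation after a dose interruption of 7 days or more. The subject is observed for 4 hours after the first re-initiation dose and assessed against the Table 4 discharge criteria at Hour 4. "Subjects not meeting the discharge criteria will require extended monitoring as described below".

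Three bullets under Extended Cardiac Monitoring matter here:

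- **Medical Monitor bullet.** The Medical Monitor is contacted if Table 4 is still not met after at least 4 hours of extended monitoring. The bullet says nothing about stopping treatment or withholding the next dose.
- **General return bullet.** "Any subject who requires extended monitoring on the first re-initiation day must return on the second re-initiation day for the second dose", with monitoring repeated as on the first day. The only stop it names is failure of Table 4 at 4 hours after that second dose.
- **Symptomatic-event bullet.** This covers symptoms in the 4-hour period that are not linked to a heart-rate reduction or a relevant ECG change. It allows discharge if Table 4 is met, also sends these subjects back for the second dose, and again places its stop after that dose.

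The stop rules are elsewhere. In Section 5.1 the mandatory list opens: "A subject's double-blind treatment must be discontinued for any of the following reasons". Two of its entries can be met on the first re-initiation day:

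- a treatment-related cardiovascular symptomatic event "associated with reduction of the heart rate or associated with clinically relevant ECG changes at any time during the 4-hour monitoring period";
- "Subjects who have not met the discharge criteria on the first day of re-initiation of treatment after ≥ 4 hours of extended monitoring".

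Table 5 in Section 9.4.1 repeats both ("associated with reduction of the heart rate or associated with clinically relevant 12-lead ECG changes at any time during the 4-hour monitoring period"; "Subjects who have not met the discharge criteria on the first re-initiation day after ≥ 4 hours of extended monitoring"). The First Dose Cardiac Monitoring text adds that subjects with such a symptomatic event "at any time during the 4-hour monitoring period must be discontinued from treatment (Table 5").

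**The concern.** The general return bullet is mandatory and covers everyone who enters extended monitoring. Some of those subjects will already have met a mandatory stop criterion that day. For them one instruction orders a dose and another forbids it, and the protocol does not say which governs. Section 9.1 rules out waivers, so a site that follows either instruction departs from the other.

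At stake is a repeat dose in a subject who has just met a cardiac stop rule. Section 1.3 lists first-dose bradycardia and AV block among the common adverse events reported for this drug class. The monitored re-initiation procedure is where the protocol should be least ambiguous about the next dose.

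**Working it through.** There is no plan figure to reproduce. The check traces each first-day course through the return instructions and the stop rules.

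**Timing**

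- Group (a), still failing discharge after extended monitoring: 4 h standard + at least 4 h extended = criterion met at 8 h or more after the first re-initiation dose.
- Group (b), symptomatic event with heart-rate reduction or relevant ECG change: criterion met between 0 and 4 h. If Table 4 is also failed at Hour 4, the subject enters extended monitoring.

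**Courses on the first re-initiation day**

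| Course | Return instructions in 9.4.1 | Section 5.1 and Table 5 | Result |
|---|---|---|---|
| 1. No (b) event; fails Hour 4; meets Table 4 by the 4-hour extended check | Return | No stop | Consistent |
| 2. Fails Hour 4; still fails after at least 4 h of extended monitoring | Return (general bullet) | Stop, group (a) | Conflict |
| 3. (b) event in the first 4 h; fails Hour 4 | Return (general bullet); symptomatic-event bullet does not apply to that event | Stop, group (b) | Conflict |
| 4. Symptoms unrelated to heart rate or ECG that persist through at least 4 h of extended monitoring | Return (both bullets) | Stop, group (a) | Conflict with both bullets |
| 5. (b) event; meets Table 4 at Hour 4 | Neither bullet applies | Stop, group (b) | Consistent |

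Course 3, worked through: treatment-related dizziness with reduced heart rate at Hour 2, Table 4 failed at Hour 4 and met at Hour 6. Treatment must stop because of the Hour 2 event. The general bullet nevertheless calls for a second dose, because the subject needed extended monitoring. The Medical Monitor bullet is not triggered, since the subject met Table 4 after 2 hours of extended monitoring.

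Course 4 depends on Table 4 requiring the absence of cardiac symptoms. Persistent symptoms therefore fail discharge even when heart rate and ECG are unremarkable, and the subject reaches group (a). The symptomatic-event bullet could be read narrowly, so that only discharged subjects return. That does not remove the conflict: monitoring continues until Table 4 is met, so a subject can fail at 8 h, be discharged later, and still be told to return.

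**Frequency.** The documents give no rate for interruptions of 7 days or more, for Hour 4 failure, or for either stop criterion. No expected count can be derived for the planned 35 or so subjects.

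**The case against.** The strongest reply is that the stop rule is already written on both sides of the return bullets: in Section 5.1, under First Dose Cardiac Monitoring, and in Table 5, whose lead-in refers to Section 5.1 for the complete list of reasons. A subject who has been stopped has no second dose to return for, so the sensible reading confines the return bullets to subjects still on treatment. Table 5 also refers to the second day only as applicable, which fits a day that not everyone reaches. For course 3 the stop falls due before Hour 4, so later monitoring can be read as observation only.

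Much of this stands, and most sites would probably let the stop prevail. But that is an inference. No clause states it, and the general bullet's own stop comes only after the second dose.

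The Medical Monitor is a real safeguard for group (a), because contact is required when that criterion is met. It is weaker for group (b). There, Table 5's lead-in and footnote call for contact over a discontinuation, which presupposes that the site has recognised one.

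A reader might infer from the symptomatic-event bullet's limited scope that it is already sound and that only the general bullet needs amending. The text does not support that. Its limit excludes group (b) only, and course 4 still reaches group (a) and a return instruction.

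**Conclusion.** The conflict is present in the text: the general return bullet overlaps both first-day stop rules, and the symptomatic-event bullet overlaps the failed-discharge rule. It should be corrected as a low-frequency dosing-safety matter. It arises only after a dose gap of 7 days or more, with Hour 4 discharge failure and a first-day stop criterion, in a study of about 35 planned subjects.

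A reader might go further and infer that the protocol lacks a cardiac stop rule, or that sites will re-dose stopped subjects. The documents support neither. The stop rules are explicit and mandatory, Table 5 follows the return bullets directly, and any second dose under these bullets is monitored as on the first day. Section 1.3 also reports no clinically significant vital-sign or ECG concerns in the earlier etrasimod studies. No efficacy analysis is affected.

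The conclusion rests on reading the return bullets as written, with no unstated precedence for the stop rules.

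**What to change.** Add the same exception to both return instructions under Extended Cardiac Monitoring: *unless a discontinuation criterion in Section 5.1 or Table 5 was met on the first re-initiation day; such subjects receive no further study treatment, the Medical Monitor is contacted, and monitoring continues until the discharge criteria are met.*

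In the sentence that follows each instruction, replace *These subjects* with *Subjects who receive the second dose*, so that the day-two stop does not appear to cover the excepted subjects.

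Leave Section 5.1 and Table 5 as they are. A subject who first meets Table 4 at the 4-hour extended check, with no other stop criterion, still returns as now intended.

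The cost is one clause and one changed sentence subject in each of two bullets, by clarification letter or with the next amendment, with the IRB/IEC submission that Section 11.2 requires for protocol modifications. No visit, procedure or data collection is added.

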9.4.2. Enrollment in Open-Label Extension Study APD334-303

Subjects whose UC condition in the opinion of the Investigator has not improved or has worsened compared with baseline assessment (obtained on or before the first dose in Study APD334-302) may be eligible for entry into OLE Study APD334-303 (Section 5.1.1).

Subjects who discontinue treatment prematurely should have an Early Termination visit as indicated in the Schedule of Assessments (Table 7). If the Early Termination visit is within 4 weeks of the last proctosigmoidoscopy and biopsy, these procedures do not need to be repeated.

^a All treatment discontinuations should be discussed with the Medical Monitor. ECG, electrocardiogram

[figure not shown]
9.5. Follow-Up Period

For subjects not participating in the OLE study, a follow-up visit will be performed at 2 and 4 weeks after the last dose of study treatment as indicated in the Schedule of Assessments (Table 7).

If the Early Termination or Study Completion visit is ≥ 2 weeks after the last dose of study treatment, the 2-Week Follow-Up visit is not required; however, the 4-Week Follow-Up visit should be scheduled and completed. If the Early Termination or Study Completion visit is ≥ 4 weeks after the last dose of study treatment, the 4-Week Follow-Up visit is not required.

If the absolute peripheral lymphocyte count is not within normal limits at the 4-Week Follow-Up visit, subjects should return for complete blood count (CBC) with differential according to local standard of care (captured as subsequent follow-up visit or unscheduled visit).

All adverse events should be recorded for 30 days after last dose of study treatment (Section 9.8.8.2.2).

9.7. Efficacy Assessments

The components of the MMS are used to calculate several of the primary, secondary, and The definitions for MMS components are outlined in Section 10.5.

9.7.1. Modified Mayo Score/Mayo Clinic Score

This study utilizes the MMS, which includes the ES, RB, and SF components of the Mayo Clinic score (MCS; Appendix 3) to assess UC disease activity in support of the primary and secondary endpoints. The total score range of the MMS is from 0 to 9, with each component ranging from 0 to 3 (0 = normal, 1 = mild, 2 = moderate, 3 = severe).

The MMS requires daily subject-reported RB and SF scores; therefore, the importance of daily recording of RB and SF by subjects in their daily eDiary should be stressed by the Investigators.

Endoscopy will be used to visualize the mucosa to enable calculation of the ES.

Endoscopic score (ES): The ES reports the worst appearance of the mucosa on flexible sigmoidoscopy or colonoscopy, on a 4-point scale (Appendix 3). Consistent with regulatory advice, this study excludes friability from the definition of an ES of 1. The ES will be determined by a blinded central reader.

Rectal bleeding (RB): The RB subscore is a subject-reported measure. This item reports the most severe amount of blood passed per rectum in a 24-hour period, on a 4-point scale (Appendix 3). The subject will record this in their daily eDiary. The method for calculating the RB subscore is described in Section 9.4.

Stool frequency (SF): The SF subscore is a subject-reported measure. This item reports the number of stools in a 24-hour period, relative to the normal number of stools for that subject in the same period, on a 4-point scale (Appendix 3). A stool is defined as a trip to the toilet when the subject has either a bowel movement, passage of blood alone, passage of blood and mucus, or passage of mucus only. The total number of stools passed in a 24-hour period will be recorded by the subject in a daily eDiary. The reference "normal" SF for that subject will be carried over from the parent Study APD334-302 and is the number of stools in a 24-hour period when the subject is in remission. If the subject has never achieved remission, the reported SF before initial onset of signs and symptoms of UC will be used as the reference SF. The method for calculating the SF subscore is described in Section 9.4.

Physician's Global Assessment (PGA): The PGA is a physician-reported measure that is a component of the MCS and is used in the calculation of the total Mayo Score. The PGA summarizes the Investigator's assessment of the subject's UC disease activity on a 4-point scale (Appendix 3). The Investigator will record the PGA in the site tablet at the specified study visits (Table 7). Consistent with regulatory guidance, the PGA will not be used for primary or secondary efficacy assessment in this study.

9.7.1.1. Endoscopy

A flexible proctosigmoidoscopy, performed with a video endoscope following cleansing preparation (oral or rectal cathartic), will be performed at the Week 52/Early Termination visit. Additional proctosigmoidoscopies may be performed to confirm disease worsening and are required for qualification into the OLE (Section 5.1.1).

To ensure quality data and standardization, the same endoscopist should be used throughout the study wherever possible. Endoscopy images will be obtained during each endoscopy and will be sent for central reading and determination of the Mayo endoscopic score. A detailed image review charter from the central reading laboratory will outline the endoscopic procedures, video

recordings, and equipment. For each subject, a video recording of the entire endoscopic procedure will be performed using an acceptable storage medium. The endoscopic recordings will be read centrally in a blinded manner for mucosal lesions and endoscopic severity by a qualified gastroenterologist according to the image review charter. The ES will be evaluated by the Investigator and the central reader. The central read will be used for determination of efficacy endpoints; however, treatment decisions will be made by the treating Investigator.

Repeated flexible proctosigmoidoscopy may be permitted by the Sponsor when the central reader indicates that the video endoscope data were acquired incorrectly or did not meet the minimal required quality standards.

9.7.1.2. Endoscopic Biopsy

Biopsies will be obtained at each endoscopy to support assessment of the histopathology endpoints and, where permitted, for the assessment of occurrence. Up to 4 biopsy pairs (ie, total 8) will be collected from the most affected area 15 to 25 cm from the anal verge. For subjects with proctitis only at baseline of Study APD334-302, biopsies should be taken 8 to 10 cm from the anal verge.

[figure not shown]
Detailed instructions for endoscopic biopsies (eg, number of biopsies, anatomic site, normal or inflamed mucosa) will be provided.

[figure not shown]
Biopsy samples will be processed by a central laboratory and histopathologic scoring using the Geboes, Robarts, and Nancy histopathology (Appendix 4) indices will be performed by a blinded central histopathology reader (Geboes 2000, Marchal-Bressenot 2017, Mosli 2017).

[figure not shown]
Biopsy specimen transfer, processing, slide preparation and digitization of slides for histopathologic scoring procedures will be detailed in a histopathology manual. Histopathology results will not be made available to study sites.

